35 STUDY RISKS

Risks include those risks related to taking HAMS-AB, having blood draws, mixed meal tolerance tests (MMTT), risk of CGM use, and the possible loss of confidentiality.

Risks of Taking HAMS-AB:

Given that most youths in the United States are consuming less than the recommended dietary intake of fiber, we anticipate the following risks:

- Likely (reported in >20% of patients): initial abdominal discomfort, increase in frequency of bowel movements, although not to the extent of causing diarrhea. These mild intestinal symptoms will likely last for only the first few days and are self-limited without intervention.

Risk of Blood Draws:

The insertion of a needle can cause some local pain and can result in bruising. Blood draws can in rare instances cause lightheadedness or fainting. There is also a risk of infection. To mitigate these risks, blood draws will be performed by trained technicians or nurses using standard aseptic techniques.

Risk of MMTT:

There are no known risks to an MMTT, but the taste of the Boost may not be well tolerated. Some persons may experience nausea after drinking Boost. Subjects with milk or soy allergies will be excluded to avoid any allergic

reactions to Boost. If the blood glucose is high at the end of the test, subjects will be instructed to give an insulin correction dose.

Risks related to CGM use:

The CGM/sensor may produce pain when it is inserted into the skin. There is a low risk for developing a local skin infection at the site of the sensor needle placement. Itchiness, redness, bleeding, and bruising at the insertion site may occur as well as local tape allergies.

Loss of Confidentiality:

There is the unlikely chance that health information is viewed by someone outside of the research team who is not authorized to see health information. All files will be kept in locked cabinets within a locked room. Any electronic data will be protected by password systems.

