6.3 SCHEDULE OF EVENTS

Study Phase	Screening	Baseline- Intervention	Washout	Crossover- Intervention	Follow-Up	Early Termination Visit
Visit Number	1	2	3	4	5	
Visit Window		≤30 days after Visit 1	+/- 3 days 28 days after Visit 2	+/- 3 days 28 days after Visit 3	+/- 3 days 28 days after Visit 4	
Informed consent/Accent	X					
Inclusion/Exclusion criteria	X					
Historical Data/Demographics*	X					
Pancreatic Autoantibodies †	X					
Random C-peptide concentration††	X					
Randomization		X				
Pregnancy test**	X	X	X	X	X	X
Current Medical data***		X	X	X	X	X
Pubertal Tanner staging with physical exam	X					
Ht/Wt measurement and vitals	X	X	X	X	X	X
Supervised CGM insertion (and training, if applicable on use) †††		X		X		
C-peptide by 2-hr MMTT††††			X		X	X
HbA1c		X			X	X
Blood samples for biomarkers (PI:C and INS DNA)		X	X	X	X	X
Provision of HAMS-AB		X		X		
CGM download			X		X	X
Stool samples****		X	X	X	X	X
Whole blood for additional T1D testing		X	X	X	X	X
Serum and plasma for storage^		X	X	X	X	X
Adverse event assessment*****		X	X	X	X	X
Dietary Assessments*****		X	X	X	X	X
Verbal Diet recall	X					
Sampling of prebiotic	X					

Data Collection:

***Historical data:** Date of birth, sex, Race/Ethnicity, date of diagnosis of T1D.

**To be done in girls of reproductive potential.

*****Current Medical Data (All visits except screening):** Medication use including types of insulin, means of insulin administration, and total daily insulin dose (u/kg body weight, averaged over the 3 days prior to each study visit), use of other medications.

******Stool samples** will be collected at home using a kit (Zymo feces catcher and RNA/DNA shield fecal collection tubes) within 3 days of presentation to each visit.

*****Participants will be assessed for **safety** with questions regarding general well-being as well as specific questions to evaluate for adverse events. Participants will also be questioned about stool form and frequency, gastrointestinal symptoms, fevers, or infection.

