*******Dietary Assessments** will be ideally obtained using the Automated Self-Administered 24-Hour (ASA24) dietary assessment tool [46-48], a web-based tool for administering automatically coded, self-administered recalls/food records. This will allow assessment of dietary fiber intake along with other dietary components. Participants will be asked to fill these in for the 24 hrs. diet recall prior to each stool collection in a time frame of +/- 3 days from the stool sample collection. This can also be completed during the study visit. Diet diaries will be accepted in lieu of the online questionnaire. Participants will be asked to record all meals and snacks, time of day, number of servings, major food components or description (for example chicken or protein), estimated portion sizes and whether they completed the meal or not, and any drinks including water.

†Pancreatic autoantibodies to be tested only in those with no evidence of being tested for antibodies in their medical chart to confirm T1D.

††Random, non-fasting c-peptide: C-peptide level will be analyzed at Indiana University Translation Core Lab using a two site immuno-enzymometric assay using a Tosoh 2000 auto-analyzer (TOSOH, Biosciences, Inc., South San Francisco, CA). The C-peptide assay is calibrated against the WHO IS 84/510 standard and has a sensitivity level of 0.05 ng/mL.

†††At visit 2 (baseline/intervention) and 4 (crossover), a blinded CGM sensor will be inserted in those participants who are not currently using a CGM as part of their routine care. Training will be provided on calibration of the sensor, its use in blinded mode, and sensor insertion. Participants will be reminded to insert a sensor at home after approximately 14 days and continue using the blinded sensor for an additional 14 days. Participants will use their own home blood glucose meter or (if had been previously using one) CGM for regular blood glucose monitoring. The participant will return after 4 weeks to assess the CGM data. CGM must be used for at least 200 hours (equivalent to 8.3 days out of 14 days)

††††C-peptide by 2-h MMTT: 2-hour MMTT will be performed using the standardized protocol utilized by the TrialNet Centers [51]. The early discontinuation MMTT will only be done if it has been at least 6 weeks since the last MMTT.

^Serum and Plasma for storage – subject has option to consent or deny storage. Will be used for future type 1 diabetes research assays.

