6.4 STUDY VISITS

Visit 1 – Screening

This visit will be at the hospital or research center. It will last approximately 1-2 hours and will include:

- Obtain informed consent/assent documents and determine inclusion and exclusion criteria
- Measurement of height and weight to determine BMI percentile eligibility and physical exam including pubertal staging
- Obtaining Vital signs (heart rate, temperature, blood pressure, and respiratory rate)
- Obtaining medical history
- Dietary assessment by verbal recall
- Obtaining blood sample (approximately 1.5 tablespoon) – Random non-fasting c-peptide, pancreatic autoantibodies if not previously done to confirm T1D diagnosis
- For female adolescents: urine will be collected for a pregnancytest
- Subject to sample prebiotic for palatability to ensure compliance

Visit 2 – Baseline-Intervention

This visit will be at the hospital or research center. It will last approximately 1-2 hours and will include:

- Measurement of weight and bedside nurse assessment such as general appearance, respiratory and cardiac assessment.
- Obtain vital signs (heart rate, temperature, blood pressure, and respiratory rate)
- Collecting a diet history (diary or questionnaire)
- Collecting Adverse Events (if applicable)
- Obtaining medical history and insulin use

Obtaining blood samples (approximately 2 tablespoons) – HbA1c, Serum biomarkers of beta cell stress and death (PI:C and INS DNA), other T1D testing, and serum and plasma for storage.

- Some of the blood will be stored for future T1D research use

- CGM placement and training for participants not currently using one.
- For female adolescents: urine will be collected for a pregnancytest
- Collecting stool samples prior to or the morning of the visit (a stool collection kit will be shipped to the participants once eligibility is confirmed)
- Study Randomization to either supplement or standard of care diabetes management and a diabetic diet.
– Supplement (HAMS-AB) will be provided and will be taken by mouth twice daily with food such as apple sauce or oatmeal as described in Section 6.2. Instructions will be provided for recommendations on a healthy diabetic diet.
- A new stool collection kit will be provided for the next visit

Visit 3 - Washout

This visit will be at the hospital or research center. It will last approximately 2-4 hours and will include:

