6.5 ONGOING DIABETES MANAGEMENT

All study participants will have a treating endocrinologist who is primarily responsible for their diabetes care. In general, the expectation is that all participants will receive at least three injections of insulin daily, including short- and long-acting insulin preparations, or will utilize continuous subcutaneous insulin infusion (CSII, insulin pump). As part of diabetes monitoring during the subjects' participation, we will encourage participants to check glucose levels at least four times daily if using blood glucose monitor and if not already using a CGM. **At the time of visits the study team** will suggest changes that they believe would improve the glucose control, if necessary. Letters summarizing the study visit will also be sent to the endocrinologist after parental agreement.

In addition, insulin use, hypoglycemic events, and any episodes of ketoacidosis will be captured at each visit on the appropriate CRFs.

Participants will be requested to record the amount of insulin they have used during the 3-day period immediately preceding each study visit. Insulin use logs will be provided to participants at each study visit and collected at the next visit. These logs will serve as the source documents.

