7.3 ADVERSE EVENTS

An adverse event is defined as any unintended or abnormal clinical observation that is not of benefit to the patient. Either the condition was not present prior to exposure to study supplement, or it has worsened in intensity or frequency following exposure to the study supplement. Adverse events will be graded according to the National Cancer Institute (NCI) Common Terminology Criteria v5.0.

https://ctep.cancer.gov/protocolDevelopment/electronic_applications/docs/CTCAE_v5_Quick_Reference_5x7.pdf

Any suspected or confirmed toxicity should be reported immediately (within 24 hours) to the principal investigator.

Hypoglycemic and hyperglycemic events that are seen as part of daily diabetes management will not be considered adverse events unless they result in hospitalization

Principal investigators (PI) will report to the IRB as soon as possible, but in all cases within 5 working days from notification any event that appears on the List of Events that Require Prompt Reporting to the IUPUI IRB.

List of Events that Require Prompt Reporting to the IUPUI IRB: Any of the following:

- Event (including adverse events, injuries, side effects during the research study), which in the opinion of the PI
 - caused harm to one or more subjects or others, or placed one or more subjects or others at increased risk of harm; AND
 - was unexpected; AND
 - was related to the research procedures

Note: After the study is closed with the IRB, these events will only be reported if they are profound, or they demonstrate long-term risks that would necessitate notifying subjects.

- Protocol deviation/violation (as defined under this policy)
- Change to the protocol taken without prior IRB review to eliminate apparent immediate hazard to a research subject (e.g., purposeful and for subject safety)
- Complaint of a subject that indicates unexpected risks, or complaint that cannot be resolved by the research team
- Interim findings and safety monitoring reports that indicate an unexpected change to the risks or potential benefits of the research, in terms of severity or frequency
- Publication in the literature that indicates an unexpected change to the risks or potential benefits of the research
- Change in FDA labeling or withdrawal from marketing of the supplement used in this research study
- Noncompliance (as defined in this policy)

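### No adverse event question or symptom record covers the first days of HAMS-AB, when its likely GI symptoms are expected; the first scheduled question falls on day 25 to 31

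*Combined protocol and SAP*

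**What the plan says.** All references are to the combined protocol and SAP.

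- **Expected risk.** Section 3.5 (Study Risks) gives one class of supplement risk: "Likely (reported in >20% of patients): initial abdominal discomfort, increase in frequency of bowel movements". On timing it adds: "These mild intestinal symptoms will likely last for only the first few days and are self-limited without intervention".
- **Start of dosing.** Section 6.4 hands out the supplement at Visit 2, or at Visit 4 for those who receive it second: "Supplement (HAMS-AB) will be provided and will be taken by mouth twice daily with food such as apple sauce or oatmeal".
- **Next visit.** Section 6.3 (Schedule of Events) sets Visit 3 at +/- "3 days 28 days after Visit 2" and Visit 5 at +/- "3 days 28 days after Visit 4".
- **Adverse event questions.** The same table marks adverse event assessment at Visits 2, 3, 4, 5 and early termination. Its footnote includes direct questions on stool form and frequency and on GI symptoms.
- **Between visits.** The CGM footnote in 6.3 has one prompt, for participants who do not already use a CGM: "Participants will be reminded to insert a sensor at home after approximately 14 days". No safety question is attached to it. Section 6.5 has an insulin log, issued at each visit and collected at the next: "Participants will be requested to record the amount of insulin they have used during the 3-day period immediately preceding each study visit".
- **Use of the data.** Section 7.3 grades events by CTCAE v5.0 and defines an event by its appearance or worsening after exposure. Section 8.0 (Statistical Considerations) reports each event as a proportion and names mild GI symptoms as the example.

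**The concern.** The plan expects its main named supplement effect at one end of a 4-week period and asks about it at the other. A symptom that came and went in the first few days must be remembered, dated and graded weeks later by participants aged 11 to 17 and their families. They also know which period was the supplement, because section 6.2 compares HAMS-AB plus diet with diet alone and has no placebo. Recall of this kind can lose brief mild events. It can also be coloured by knowing the treatment.

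At stake is the quality of the planned GI adverse event proportions, and of the onset, duration and grade that the definition and grading in section 7.3 call for. The efficacy endpoints are not affected.

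**Working it through.** **Inputs.** Next visit 28 +/- 3 days after dosing starts (6.3); two doses a day (6.2); 56 doses per supplement period (3.2); 12 participants, each taking the supplement once (8.0); likely class >20% (3.5). The plan does not say how many days the first few days are, so 3, 5 and 7 are assumed.

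**1. The plan's own period length.** 28 days x 2 doses = 56 doses, as section 3.2 states. Twenty per cent of 56 is 11.2, given there as 11. The supplement period is therefore 28 days, consistent with the visit table.

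**2. First scheduled question after dosing starts.** Count the dispensing visit as day 0.
- Supplement first: dosing starts after Visit 2, and the next question is at Visit 3, day 28 - 3 = 25 to 28 + 3 = 31.
- Supplement second: dosing starts after Visit 4, and the next question is at Visit 5, again day 25 to 31.

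The assessments at Visits 2 and 4 come before the daily dosing that those visits start. The palatability tasting at screening is not counted as dosing.

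**3. Recall gap** = visit day minus symptom day.

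| Symptoms end on day (assumed) | Visit on day 25 | Visit on day 31 |
|---|---|---|
| 3 | 25 - 3 = 22 days | 31 - 3 = 28 days |
| 5 | 25 - 5 = 20 days | 31 - 5 = 26 days |
| 7 | 25 - 7 = 18 days | 31 - 7 = 24 days |

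From an onset on day 1 the gap is 25 - 1 = 24 to 31 - 1 = 30 days. The range over all cases is 18 to 30 days (18/7 = 2.6 to 30/7 = 4.3 weeks), or roughly 3 to 4 weeks.

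**4. What else could record symptoms in between.** The insulin log covers only the 3 days before a visit, which is the wrong end of the period. The sensor reminder comes at about day 14, reaches only some participants and carries no safety question. No symptom diary, safety call or interim visit is described.

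**5. How sensitive 12 participants are.** One participant is 1/12 = 8.3 percentage points. At exactly 20%, 12 x 0.20 = 2.4 participants would have symptoms, and the chance that at least one is recorded under full capture is 1 - 0.80^12 = 93%. The documents give no capture rate, so the rates below are assumptions and not estimates.

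| Assumed capture | Expected reports | Chance of at least one report |
|---|---|---|
| 75% | 2.4 x 0.75 = 1.8 | 1 - 0.85^12 = 86% |
| 50% | 2.4 x 0.50 = 1.2 | 1 - 0.90^12 = 72% |
| 25% | 2.4 x 0.25 = 0.6 | 1 - 0.95^12 = 46% |

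**The case against.** The strongest defence is proportionality. The expected symptoms are mild and self-limited, and section 8.0 calls the study minimal risk. Tolerability is not an endpoint in section 3.4, and the sample size is justified by effect sizes for efficacy. Visits ask directly about stools and GI symptoms, which helps recall. With 12 participants the proportion is imprecise anyway: 3 of 12 has an exact 95% interval of about 5% to 57%. All of this stands. It limits the weight of the point but does not close the gap in timing.

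A reader might also infer three stronger things that the documents do not support.

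- *That 24-hour reporting cannot work.* Section 7.3 says: "Any suspected or confirmed toxicity should be reported immediately (within 24 hours) to the principal investigator". It does not start the clock at onset, so the rule can run from awareness. It names neither the reporter nor the clock start, but that does not make it unworkable. Instructions to families on whom to contact may lie in consent or contact pages that are not available here, so their absence cannot be held against the plan.
- *That symptoms are captured only by recall.* Unsolicited reports are not ruled out. Section 5.3 brings a participant with a medically important event back for an exit visit, where adverse events are assessed, and section 7.1 contemplates severe events away from a medical facility.
- *That repeated low glucose is noticed only after the period ends.* Participants keep their own meter or CGM for routine monitoring (6.3). Those without a CGM are encouraged to test at least four times daily, and all have a treating endocrinologist (6.5).

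A final fair objection is that a diary does not remove knowledge of treatment. That is true. It shortens recall and makes the two periods comparable in method, and no more.

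**Conclusion.** The point holds as a weakness in how early tolerability is ascertained, not as a failure of safety reporting. The day 25 to 31 timing follows directly from section 6.3 and is the same in both sequences. The recall gap of roughly 3 to 4 weeks depends only on reading the first few days as 3 to 7.

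The direction and size of any error are not known from the documents. Brief events may be forgotten, and open treatment may push reports either way. The capture rates in the check show only how sensitive a sample of 12 is and should not be quoted as expected under-reporting. Nor is the >20% class a threshold that the trial must meet; it describes an expected risk.

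The change is worth making because it is cheap and improves an output that the plan already intends to report.

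**What to change.** Add one page to the log sheet that section 6.5 already issues at each visit and collects at the next. It would hold a daily tick-record for days 1 to 7 of each 4-week period, covering GI symptoms, stool frequency and missed doses. Use the same page in the HAMS-AB and control periods, with the dose line marked not applicable under control, so that both proportions come from the same instrument. State in section 8.0 that this record is the source for the GI adverse event proportions, with the visit questions covering the rest of the period.

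Filled in daily, the record reduces the gap for a day-1 symptom from 24 to 30 days to less than a day. If it is completed in one sitting on day 7, the gap is 7 - 1 = 6 days. If it is filled in just before the visit, nothing is gained, so the instructions should ask for same-day entry. The missed-dose line covers 7 x 2 = 14 of the 56 doses, so it sets early missed doses beside symptoms but cannot by itself settle the replacement rule in section 3.2.

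The cost is slightly more participant burden and more mild events on record. No visit or staff contact is added, and dosing and clinical management do not change.

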36 STUDY BENEFITS

While receiving HAMS-AB, there are potential benefits in reduction of β -cell stress for these patients. Since the gut dysbiosis may be important in the pathogenesis of T1D, accentuate β -cell stress, and have a role in the complications of the disease, these studies are of scientific importance. The benefits to be derived by mankind are expected to be substantial and may lead to advances in the prediction, prevention, and treatment of type 1 diabetes. If this study indicates that treatment can safely preserve beta cell health, then it will be a major advance in the care of diabetes.

37 INCLUSION OF CHILDREN

Type 1 diabetes is a disease that typically has its onset in children, adolescents, and young adults. Because we are interested in examining the role of the HAMS-AB and the gut microbiome in adolescents with T1D (and potentially eventually those at risk for developing T1D), adolescents will be studied to have data in a relevant population. As part of the consent process, in addition to consent from the parent, assent for studies and samples from all participants will be obtained.

4.0 – STUDY SUPPLEMENT**4.1 STRUCTURE AND NOMENCLATURE**

CAS Registry No.:	none
Chemical Name:	high amylose maize starch
Chemical Family:	Starch
Molecular Weight:	>1000
Synonyms:	HYLON® VII

4.2 PHYSICAL AND CHEMICAL PROPERTIES

Pure Substance or Mixture:	Pure
Appearance (physical state):	Powder.
Color:	White
Odor:	Starch
Odor threshold:	Not available
Molecular Weight:	> 10000
pH:	Not available
pH in (1%) Solution:	Approximately 5.5
Melting Point/Freezing Point (°C):	Not available
Relative Density:	Not available

Specific Gravity 1.5
Solubility(ies) in Water: Insoluble

4.3 STABILITY AND REACTIVITY

Reactivity:	Not expected to be reactive
Chemical stability:	Material is stable under normal temperatures and pressures.
Possibility of hazardous reactions:	Hazardous polymerization will not occur.
Conditions to avoid (e.g., static discharge, shock, or vibration):	None known
Incompatible materials:	None known
Hazardous decomposition products:	This product does not undergo spontaneous decomposition. Typical combustion products are carbon monoxide, carbon dioxide, nitrogen, and water.

4.4 CLINICAL STUDIES – MECHANISM OF ACTION

HAMS appears to work by altering the gut microbiome profile and improving glycemia and insulin sensitivity [26, 27]. Additionally, the FDA has concluded that there was scientific evidence for a qualified health claim that HAMS reduced risk of type 2 diabetes development in adults.

